16.0 Reporting Adverse Drug Reactions

16.1 Adverse Event Definitions

16.1.1 Clinical Adverse Events

A clinical adverse event is any unfavorable or unintended sign, symptom or disease temporally associated with the use of the study drug occurring in a research patient treated with the study drug during treatment or post-treatment follow-up period, regardless of causality assessment. This includes adverse clinical or laboratory findings, intercurrent illness, or an exacerbation or progression of a disease/condition present at baseline.

An adverse event is unexpected if it is not listed in the current labeling for the study drug. An adverse event is considered non-serious if it does not meet any of the serious criteria below.

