3.0 Study Design and Eligibility Criteria

3.1 Study Design

This is a nonrandomized, open label, multicenter phase II trial to evaluate the efficacy of pazopanib in combination with a NSAI in patients with advanced breast cancer.

Patients with metastatic breast cancer progressing or relapsing on a NSAI will be eligible for enrollment in this study. Progression must be documented by radiographic studies. This will be a two-step protocol; 14 patients will be enrolled initially. If at least 1 response (response defined as clinical benefit) is observed in the first 14 patients at 12 weeks, we will proceed to

the second stage, where an additional 13 patients will be enrolled. We plan to enroll a total of 30 patients at 2 sites: UCSF and Yale Cancer Center (Yale), expecting that up to 3 patients will be un-evaluable due to unexpected events.

Treatment will consist of pazopanib, 800 mg a day by mouth and continuation of the NSA1 (letrozole, 2.5 mg a day, or anastrozole, 1 mg a day) the patient was taking at the time of progression. This treatment will be continued until progression or toxicity. Dose reduction of pazopanib for toxicity will be allowed. Patients will be evaluated by serial radiographic studies as well as circulating tumor cells. The primary endpoint is clinical benefit rate at 12 weeks.

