(C). ALT $>8.0 \times$ ULN without bilirubin elevation (defined as total bilirubin $<2.0 \times$ ULN or direct bilirubin $\leq 35\%$) and without hypersensitivity symptoms (e.g., fever, rash), not attributed to malignancy.	
1st occurrence
 
1. Discontinue pazopanib until toxicity resolves to \leq Grade 1 or baseline. Report the event to Novartis as an SAE within 24 hours of learning of its occurrence (section 16.2, SAE reporting), and complete the eCRF liver event forms. Make every reasonable attempt to have subjects return to the clinic within 24 to 72 hours for repeat liver chemistries and liver event follow up assessments. Pazopanib may only be restarted following recovery if toxicity is clearly unrelated to study drug (e.g. alcohol or significant acetaminophen ingestion)2. Work up for other etiologies as clinically indicated .3. Monitor subject closely for clinical signs and symptoms; perform full panel LFTs weekly or more frequently if clinically indicated until alanine aminotransferase (ALT)/aspartate aminotransferase (AST) reduced to Grade 1.

Event	Dose Modification Algorithms
(D). ALT >3.0 x ULN with concomitant elevation in bilirubin (defined as total bilirubin <2.0 x ULN; with direct bilirubin >35%) not related to disease progression, or with hypersensitivity symptoms (e.g., fever, rash).	
 1. Discontinue pazopanib immediately, report the event to Novartis as an SAE within 24 hours of learning of its occurrence (section 16.2, SAE reporting), and complete the eCRF liver event forms. Make every reasonable attempt to have subjects return to the clinic within 24 hours for repeat liver chemistries and liver event follow up assessments. 2. Consult a gastroenterologist / hepatologist and perform the following assessments to identify potential co-factors: 
 • Eosinophil count • Viral serology for hepatitis A, B, C and E, cytomegalovirus, Epstein-Barr virus IgM antibody, or heterophile antibody, or monospot testing) • Anti-nuclear antibody, anti-smooth muscle antibody, anti-mitochondrial antibody • Serum creatinine phosphokinase for possible muscle injury caused LFT elevation • Liver imaging (ultrasound or CT scan) 3. Monitor subject closely for clinical signs and symptoms; perform full panel LFTs weekly or more frequently if clinically indicated until LFTs reduced to Grade 1.

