12.1 Endpoint Definitions

Primary endpoint:

- The primary endpoint of this study is clinical benefit (including complete response, partial response, and stable disease) of at least 12 weeks.

Secondary endpoint:

- PFS: evaluate progression free survival in patients treated with the combination of pazopanib and a NSAI in this trial
- Safety : adverse events, SAEs

Exploratory endpoints:

- Evaluate the impact of the combination of pazopanib and a NSAI on circulating tumor cells
- Evaluate the change of immune profile with the combination of pazopanib and a NSAI

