16.1.3 Serious Adverse Events

A serious adverse event (SAE) is any adverse event occurring at any dose that results in any of the following outcomes:

- death,
- life-threatening (places the subject, in the view of the investigator, at immediate risk of death from the reaction as it occurred),
- inpatient hospitalization or prolongs existing hospitalization,
- persistent or significant disability/incapacity (a substantial disruption of a person's ability to conduct normal life functions),
- birth defect/congenital anomaly,
- or any important medical event that may not result in prior listed outcomes but, based upon appropriate medical judgment, may jeopardize the subject, and may require medical or surgical intervention to prevent one of the prior listed outcomes.

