If the study has an increase of unexpected or expected Adverse Event grade 3 or 4 above the rate reported in the Investigational Brochure or package insert, the increase rate of AEs will be reported by the Study Chair to the UCSF DSMC at the time of Identification. The UCSF DSMC Chair and Study Chair will discuss the finding and proceed with a written course of action. If at any time the Study Chair stops enrollment or stops the study due to safety issues the UCSF DSMC Chair must be notified within 24 business hours via e-mail. The UCSF DSMC must receive a formal letter within 10 business days and the CHR must be notified.

If any of the above action occurs in a multiple-institutional clinical trial coordinated by the UCSF-CCC, the Study Chair will insure that all participating sites are notified.

Data and Safety Monitoring Committee Contacts:

DSMC Chair: [REDACTED]

[REDACTED]

Email [REDACTED]

Box [REDACTED]

DSMC Monitors

[name]

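### The adverse event definition takes in progression of the breast cancer under study, so one event can count both as an efficacy failure and as a safety event, and the plan does not say how to separate the two

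*Combined protocol and SAP*

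**What the plan says.** Section 16.1.1 defines a clinical adverse event broadly. It covers events "during treatment or post-treatment follow-up period, regardless of causality assessment", and it expressly includes "intercurrent illness, or an exacerbation or progression of a disease/condition present at baseline". Section 3.1 sets the baseline disease: "Patients with metastatic breast cancer progressing or relapsing on a NSAI will be eligible for enrollment in this study". No sentence in section 16 excepts that cancer.

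The SAE definition in 16.1.3 builds on the AE definition: "A serious adverse event (SAE) is any adverse event occurring at any dose that results in any of the following outcomes". The listed outcomes include death and inpatient hospitalisation, again with no exception for the cancer.

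The secondary safety endpoint in 12.1 reads only "Safety : adverse events, SAEs", with no summary measure, grade limit or attribution filter. The primary endpoint in the same section is "clinical benefit (including complete response, partial response, and stable disease) of at least 12 weeks", and PFS is the other secondary endpoint.

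Under Review of Adverse Event Rates, 16.2.2 requires a report to the UCSF DSMC if the study shows an "increase of unexpected or expected Adverse Event grade 3 or 4 above the rate reported in the Investigational Brochure or package insert".

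The only places that set malignancy or progression apart are two liver rows of Table 3 in section 7.0. Row (C) excludes events attributed to malignancy. Row (D) applies to events "not related to disease progression, or with hypersensitivity symptoms". Both are dose-modification rules.

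The recording rules differ. Section 8.4 asks for any AE, with its grade, at follow-up. Section 16.2.1 names grade 3 and above for entry in the trial database.

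**The concern.** Read as written, a patient whose cancer progresses has an adverse event by definition, and a hospitalisation or death from the cancer is an SAE. The same fact is then a failure of the primary endpoint (if it falls by week 12), a PFS event and a safety event.

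The secondary safety objective concerns the combination, and the trial has one arm. If progression-related events sit unmarked in the AE, SAE and grade 3-4 rates, those rates mix lack of efficacy with toxicity. The grade 3-4 rates are then compared with brochure or label rates, and the monotherapy safety profile described in 1.2 comes from 225 renal cancer patients. Cancer deterioration could contribute to a DSMC report or make the combination look more toxic than it is. Nothing tells the two sites whether to enter progression as an AE, so they could handle it differently.

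**Working it through.** **The plan's own figure.** Section 12.0 gives p0 = 0.05, p1 = 0.20, stages of 14 and 13, continuation with at least 1 response and success with at least 4 of 27. The probability of success is the sum over x1 ≥ 1 of P[Bin(14, p) = x1] × P[Bin(13, p) ≥ max(0, 4 − x1)].
- At p = 0.20 this is 0.807 (stated: 80% power).
- At p = 0.05 it is 0.042 (stated: below 5%).

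The design reproduces, and nothing in it depends on the AE definition.

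**Does the text allow double counting?**
- 16.1.1: progression of a baseline disease is an AE, whatever its cause.
- 3.1: the baseline disease is progressing breast cancer in every patient.
- 16.1.3: an AE with a listed outcome is an SAE.
- 12.1: AEs and SAEs are the safety endpoint, with no filter.
- 5.2 and 8.4: treatment stops at progression and follow-up runs four more weeks. 16.1.1 covers post-treatment follow-up, so early decline after progression falls inside the AE window.

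The double count therefore follows from stated rules. Grade 3-4 events can enter the 16.2.2 comparison. Deaths enter the SAE count but not a grade 3-4 rate.

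**How large could it be by week 12, among 27 evaluable patients?**

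1. *Ceiling: every failure is a progression and every progression is recorded.* Failures = 27 × (1 − p).
   - p1 = 0.20: 27 × 0.80 = 21.6 (80%).
   - p0 = 0.05: 27 × 0.95 = 25.65 (95%).
   - A trial that just succeeds: 27 − 4 = 23 (85%).

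2. *Protocol's earlier pazopanib data (section 1.2: 20 patients with metastatic breast cancer, monotherapy, median time to progression 5.3 months).* Take 12 weeks as 84/30.44 = 2.76 months and assume exponential progression.
   - Share progressed = 1 − 0.5^(2.76/5.3) = 1 − 0.697 = 0.303.
   - 27 × 0.303 = 8.2 patients.
   - The same trial reports progression as best response in 35%, which on 27 patients is 9.5.

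3. *Only grade 3 and above recorded.* The share of progressions graded 3 or above is not given, so it is assumed. Applied to the ceiling:

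| Assumed share | at p1 = 0.20 | at p0 = 0.05 |
|---|---|---|
| 10% | 2.2 | 2.6 |
| 25% | 5.4 | 6.4 |
| 50% | 10.8 | 12.8 |
| 100% | 21.6 | 25.7 |

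A 10% share of the 8.2 in step 2 would be 0.8 patients. Progressions after week 12 are not in any of these figures.

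**The case against.** A reader might infer that nearly every efficacy failure is also a safety event, so that AE incidence would be 80-95% by week 12 before any toxicity. The documents do not support that.
- The values 1 − p1 and 1 − p0 are design hypotheses for lack of benefit. They are not progression rates, and the protocol's own pazopanib data point well below them.
- Under 12.2 a patient is evaluable after two weeks of treatment, so one who then stops for toxicity or withdraws can fail without progressing.
- If the grade 3 rule in 16.2.1 governs, a progression seen only on a scan may never reach the safety data. No section assigns progression a grade. Section 8.4 points the other way, and the plan does not settle it.

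A reader might also infer that progression cannot be separated without a control arm. It can: objective status is recorded at each evaluation (9.1), so progression is identifiable patient by patient. Nor do the Table 3 rows prove that the authors meant to keep progression out of the AE data. They govern dosing for liver events, and the wording of 16.1.1 suggests deliberate breadth.

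The strongest defence is that all-cause collection combined with attribution is a coherent approach. The Site Committee reviews attribution for both sites (16.2.1), which also weakens the between-site worry, and investigators assess the relationship of each SAE to each study treatment (16.2.2). This stands as a reason not to narrow the definition. Narrowing 16.1.1 would also change what the SAE reporting duties cover, because an SAE is defined as an AE. The defence does not answer the reporting gap: neither the safety endpoint nor the brochure comparison says that attribution or progression status is used when rates are tabulated.

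**Conclusion.** The point holds in a limited form. By its stated rules, the plan lets progression of the breast cancer, and hospitalisations or deaths from it, count both as efficacy failures and in the safety endpoint. At grade 3-4 they can also enter the brochure or label comparison.

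The size of the overlap is unknown from the documents. By week 12 it is at most about 22 to 26 of 27 at the design rates. It is roughly 8 of 27 if the earlier monotherapy trial is a guide and progression is exponential, although that population differs (two to three prior chemotherapies, 70% ER-positive). It is 2 to 3 of 27 if only grade 3 and above is recorded and 10% of the ceiling reaches that grade.

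The primary analysis, alpha, power and sample size are not affected. This is a cheap improvement to how safety is reported.

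**What to change.** Leave the AE and SAE definitions and all SAE reporting duties as they are. Then:
- State in 12.1 and 16.2.2 that breast cancer progression, and events the investigator judges due solely to it, are flagged and listed separately, including hospitalisations and deaths.
- Show the AE, SAE and grade 3-4 rates, including those in the brochure or label comparison, with and without the flagged events.
- Keep events of uncertain cause in the toxicity rates.
- Reconcile the AE recording rules in 8.4 and 16.2.1, so that both sites know which grades are entered and whether progression is entered as an AE.

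The cost is an investigator judgement of cause, which is imperfect in an uncontrolled trial, plus one extra table and one listing. Showing both sets of rates limits the harm from a wrong judgement, because no event is removed from view.

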16.1.2 Laboratory Adverse Events

Laboratory test value abnormalities will not be recorded as adverse events unless they are designated as serious, require treatment, or cause premature withdrawal.

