1.2 Investigational Therapy

Pazopanib

Pazopanib is a potent, multi-targeted TKI of VEGFR-1, -2, -3, PDGFR- α and - β and c-kit, with IC₅₀ values of 10, 30, 47, 71, 84 and 74 nM, respectively[17]. It inhibits VEGF-induced VEGFR-2 phosphorylation in human umbilical vein endothelial cells (HUVEC) as well as in mouse lungs in a dose-dependent manner. Pazopanib shows significant growth inhibition of a variety of human tumor xenografts in mice, and also inhibits bFGF- and VEGF-induced angiogenesis in two mouse models of angiogenesis, the Matrigel™ plug assay and the cornea micropocket model.

To date, the safety experience includes over 1200 cancer subjects who have been treated in pazopanib studies. Over 850 subjects have received pazopanib monotherapy; the monotherapy safety profile described is based on 225 subjects with renal cell cancer treated with pazopanib. The most common AEs occurring in $\geq 10\%$ of subjects in decreasing order of frequency were diarrhea, fatigue, hair depigmentation, nausea, hypertension, dysgeusia, headache, anorexia, rash, vomiting, abdominal pain, cough, arthralgia, and constipation. Elevations in ALT of any Grade were reported in 50% of subjects with Grade 3 elevations in 6% and Grade 4 in < 1%. AST and ALT elevations occurred in parallel. Hyperbilirubinemia of any Grade occurred in 29% of subjects with Grade 3 elevations in 2%. No Grade 4 elevations have been reported. Concomitant elevations in transaminases and bilirubin have been observed in less than 1% subjects. Uncommon ($\leq 1\%$) but significant adverse events have been reported including: pulmonary embolism, venous thrombosis, hemorrhage, bowel perforation, myocardial infarction/angina, cerebrovascular accidents/TIA, atrial fibrillation, renal failure, and seizures.

Anemia, leukopenia, and thrombocytopenia were reported in 14 – 20% of subjects with Grade 3/4 abnormalities being uncommon ($\leq 2\%$). Hyponatremia of any grade was observed in 32% of subjects; with Grade 3 or 4 hyponatremia in 7% of subjects. Hyperkalemia of any grade was reported in 21% of subjects with Grade 3 or 4 hyperkalemia in 3% of subjects. Hyponatremia and hyperkalemia have not occurred concurrently in the same subject to suggest adrenal insufficiency. Increase in creatinine of any grade was reported in 25% with Grade 3 or 4 events in 1%. Elevations in amylase and lipase of any

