The most common adverse reactions (greater than or equal to 20%) were diarrhea, hypertension, hair color changes, nausea, anorexia, and vomiting. Grade 3/4 adverse reactions that differed by greater than or equal to 2% between arms were abnormal hepatic function, diarrhea, hypertension, and proteinuria. QT prolongation has been seen with pazopanib. Laboratory abnormalities occurring in >10% of patients and more commonly (>5%) in the pazopanib arm included increased transaminases, hyperglycemia, leukopenia, hyperbilirubinemia, neutropenia, hypophosphatemia, thrombocytopenia, lymphocytopenia, hyponatremia, hypomagnesemia, and hypoglycemia. Deaths due to serious adverse events include cerebrovascular accident, gastric cancer, gastrointestinal hemorrhage, hemoptysis, bowel perforation, cardiac failure, myocardial infarction, hepatic failure and pneumonia occurred more commonly in the pazopanib arm. Hepatic dysfunction is included as a boxed warning in the product label and two deaths were associated with hepatic failure.

Recently, a phase II trial was designed for patients with metastatic breast cancer, who failed 2-3 prior chemotherapy. Total 20 patients were recruited in this study, 70% were ER+, and all were Her-2/neu negative. Pazopanib monotherapy was given at 800 mg daily. One patient (5%) had a partial response, 11 (55%) had stable disease (SD) [four (20%) with SD > or = 6 months], and seven (35%) had progressive disease as their best response. One (5%) was not evaluable. The median time to progression was 5.3 months. Pazopanib did not cause significant severe toxicity aside from grade 3-4 transaminitis, hypertension, and neutropenia in three patients each (14% each) and grade 3 gastrointestinal hemorrhage in one patient (5%)[18].

Standard therapy for hormone receptor positive metastatic disease.

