The UCSF Coordinating Center provides administration, data management, and organizational support for the participating sites in the conduct of a multicenter clinical trial. The UCSF Coordinating Center will also coordinate, at minimum, quarterly conference calls with the participating sites or more frequently as needed to discuss risk assessment. The following issues will be discussed as appropriate:

- Enrollment information
- Adverse Events (i.e. new adverse events and updates on unresolved adverse events and new safety information)
- Protocol Violations
- Other issues affecting the conduct of the study

Adverse events reporting to the DSMC will include reports from both the UCSF Coordinating Center, as well as the participating sites. The DSMC will be responsible for monitoring all data entered in OnCore® at the UCSF Coordinating Center and the participating sites. The data (i.e. copies of source documents) from the participating sites will be faxed over to the UCSF Coordinating Center prior to the monitoring visits in order for the DSMC to monitor the participating site's compliance with the protocol, patient safety, and to verify data entry.

Review and Oversight Requirements

Adverse Event Monitoring

Adverse Events (AEs) will be recorded on the UCSF Helen Diller Family Comprehensive Cancer Center CTMS database, all grade 3 and above expected and unexpected AEs will be recorded and updated at each visit.

All Grade 3-5 adverse events entered into OnCore® will be reviewed on a monthly basis at the UCSF Site Committee meetings. All clinically significant adverse events must be reported to the UCSF Coordinating Center by the participating sites within **10 business days** of becoming aware of the event or during the next scheduled quarterly conference call, whichever is sooner. The UCSF Site Committee will review and discuss the selected toxicity, the toxicity grade, and the attribution of relationship of the adverse event to the administration of the study drug(s) from the UCSF Coordinating Center and the participating sites.

In addition, all suspected adverse reactions considered “serious” must be entered in OnCore® and reported to the UCSF Coordinating Center within **1 business day**. The suspected adverse reactions considered “serious” will be reviewed and monitored by the Data and Safety Monitoring Committee on an ongoing basis and discussed at the DSMC meeting, which take place every six (6) weeks.

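### Section 16.1.2, read literally, lets laboratory toxicities that change the pazopanib dose go unrecorded as adverse events, and other sections point the other way

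*Combined protocol and SAP*

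**What the plan says.** Section 16.1.2 sets the rule for laboratory values: "Laboratory test value abnormalities will not be recorded as adverse events unless they are designated as serious, require treatment, or cause premature withdrawal". There are three triggers. CTCAE grade is not one of them, and neither is interrupting or reducing pazopanib.

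Table 2 in Section 7.0 gives the dose action. For Grade 3 or 4 thrombocytopenia, pazopanib is interrupted until recovery to Grade 2 or better and restarted 200 mg lower. It is discontinued only if there is no recovery or the event recurs. Neutropenia has no row of its own. A clinically significant Grade 3 case falls to the catch-all row for other clinically significant events, which interrupts until Grade 1 or better and restarts 200 mg lower. Grade 4 in that row means discontinuation.

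Three other places bear on recording:

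- Section 16.1.1, within the definition of a clinical adverse event: "This includes adverse clinical or laboratory findings".
- Section 16.2.1: "all grade 3 and above expected and unexpected AEs will be recorded and updated at each visit".
- Section 12.1, the whole definition of the safety endpoint: "Safety : adverse events, SAEs".

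Section 16.2.2 has the Study Chair report to the UCSF DSMC if the study shows an increase in "Adverse Event grade 3 or 4 above the rate reported in the Investigational Brochure or package insert".

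**The concern.** The plan treats certain laboratory toxicities as important enough to stop the drug for a time and lower its dose. The rule for laboratory values does not require those same events to be recorded as adverse events. Safety is one of two secondary endpoints and is defined only on adverse events and SAEs. Section 12.0 plans no separate analysis of laboratory values by grade, and the rate review in Section 16.2.2 also counts adverse events. An event that never becomes an adverse event therefore drops out of both.

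Haematological toxicity of this drug is not hypothetical. Section 1.2 reports, from the 20-patient trial of pazopanib alone in metastatic breast cancer, "grade 3-4 transaminitis, hypertension, and neutropenia in three patients each (14% each". Coordinators at both UCSF and Yale enter data (Section 4.3). If they read Sections 16.1.1, 16.1.2 and 16.2.1 differently, the same blood count can be an adverse event at one site and not at the other.

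**Working it through.** The plan states no figure to reproduce on this point. The check has two parts: run typical cases through the rules, then size the events using the plan's own rates.

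**Cases against the three triggers of Section 16.1.2.** Except where noted, each case is assumed untreated and not designated serious. Permanent discontinuation of pazopanib is taken to count as premature withdrawal, which the plan does not spell out.

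| Case | Action in Section 7.0 | Trigger met? | Must it be recorded under 16.1.2? |
|---|---|---|---|
| First Grade 3-4 thrombocytopenia, recovers | Interrupt, restart 200 mg lower | None | No |
| Same, no recovery or recurrence | Discontinue | Withdrawal | Yes |
| Grade 3 neutropenia, clinically significant | Interrupt, restart 200 mg lower | None | No |
| Grade 4 neutropenia (catch-all row) | Discontinue | Withdrawal | Yes |
| ALT above 8 x ULN (Table 3, row C) | Stop, report as SAE | Serious | Yes |
| ALT above 3 and up to 8 x ULN, no bilirubin elevation or hypersensitivity (Table 3, row B) | Continue at current dose | None | No |

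The first and third rows are the gap: the dose changes and recording is not required. Some Grade 4 thrombocytopenias would be treated or judged serious and so recorded, but nothing makes that automatic. Liver chemistry has its own reporting route (Table 3 and Section 16.2.2). Neutrophils and platelets have none.

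**Do the other sections close it?** Section 16.2.1 covers Grade 3 and higher *AEs*, so it applies only once a value has been accepted as an adverse event. Section 16.1.1 does include laboratory findings, but under the heading for clinical adverse events, while 16.1.2 is the specific rule for laboratory values. No section says which prevails.

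**Size of the pool of events.** Inputs: 27 evaluable patients of 30 enrolled (Section 12.6). Grade 3-4 neutropenia in 3 of 20 patients (Section 1.2); 3/20 = 0.15, although the text prints 14%. For anaemia, leukopenia and thrombocytopenia on monotherapy in renal cell cancer, Section 1.2 says "with Grade 3/4 abnormalities being uncommon", at most 2%.

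- Neutropenia, Grade 3-4: 27 x 0.15 = 4.05 expected (30 x 0.15 = 4.5). Chance of at least one in 27: 1 - 0.85^27 = 0.988.
- The Clopper-Pearson 95% interval for 3/20 is 0.032 to 0.379. That gives 27 x 0.032 = 0.9 to 27 x 0.379 = 10.2 cases.
- Thrombocytopenia, Grade 3-4: at most 27 x 0.02 = 0.54 (30 x 0.02 = 0.6). Chance of at least one in 27: at most 1 - 0.98^27 = 0.420.

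These are counts of all such events. The number left unrecorded is this count times the share that is untreated, not serious, managed without withdrawal, and left out by the site. The documents give no part of that share. At the quoted rates, about 4 and about 0.5 are therefore ceilings. The first also includes Grade 4 neutropenias, which the table shows are already captured.

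**The case against.** The strongest reply is that the plan, read as a whole, already leads a careful site to record these events. A clinician reaches the catch-all row only after judging the neutropenia to be a clinically significant adverse event. Section 16.2.1 then has Grade 3 and higher AEs recorded, and clinically significant ones reported to the coordinating centre within 10 business days. Thrombocytopenia is a named row in a table of potential treatment-related adverse events, and that row asks for the cause to be documented. Section 9.2 grades all toxicities by CTCAE. Blood counts are scheduled and all collected data go into OnCore (Section 13.0), so the values exist.

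All of this stands. It makes the problem an unresolved conflict rather than a certain loss. It does not remove the conflict, because 16.1.2 is explicit and the safety endpoint and the rate review are defined on adverse events, not on raw values.

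A reader might infer three stronger things, none of which the documents support.

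- *That serious haematological toxicity will be lost.* The text allows omission; it does not require it, and several sections pull the other way.
- *That the rate review will miss an excess by a calculable amount.* Section 16.2.2 states no threshold or test, and the brochure and package insert are not in the documents. Section 1.2 lists adverse events separately from laboratory abnormalities, so the comparison may well be adverse events with adverse events. The recorded share is unknown.
- *That patients are under-protected because Table 2 has no neutropenia row.* The catch-all row gives a dose action. Enrolment pauses for a safety review after the fifth patient has had two weeks of drug (Section 12.4), and toxicities and dose adjustments are discussed monthly (Section 16.2.1).

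**Conclusion.** The point holds as a recording conflict. Followed to the letter, 16.1.2 does not require an adverse event entry for an untreated, non-serious Grade 3-4 thrombocytopenia that recovers, or for a clinically significant Grade 3 neutropenia, even though each leads to a pazopanib hold and reduction. Such events can be missing from the safety endpoint and from the Grade 3-4 rate review, and the two sites may record them differently.

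The size is bounded only loosely: at the quoted rates, no more than about 4 neutropenias (Grade 4 included) and about 0.5 thrombocytopenias in 27 patients. This assumes that rates from pazopanib alone carry over to the combination; the neutropenia rate comes from 20 patients who had failed 2-3 prior chemotherapies. No quantified effect on the rate review is claimed. The primary endpoint and individual care are not affected. This is a cheap improvement to the completeness and consistency of the safety data, not a fault that undermines the trial.

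**What to change.** Add one sentence to Section 16.1.2: *A laboratory value of CTCAE Grade 3 or higher, or one for which pazopanib is held, reduced or stopped, is recorded as an adverse event whether or not it is treated.*

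Leave the dose rules in Section 7.0 unchanged. Text assigning laboratory values to the catch-all row by grade would carry that row's discontinuation at Grade 4 to values that nobody has judged clinically significant. That is a clinical decision for the sponsor, not a recording matter.

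The cost is an amendment and a modest number of extra entries. No new test is needed, because chemistry, liver tests and blood counts with differential are already scheduled (Section 8.0), and entries for patients already treated can be completed from collected values. The entries would include Grade 3 ALT or bilirubin values that do not follow the SAE route.

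As a rough guide, take the Section 1.2 monotherapy rates for tests done here: sodium 7% ("with Grade 3 or 4 hyponatremia in 7% of subjects"), ALT 6% (Grade 3), potassium 3%, bilirubin 2% (Grade 3), creatinine 1%, and three blood-count items at up to 2% each. These sum to at most 25%, and 27 x 0.25 = 6.75 first events. With neutropenia at 15% in place of leukopenia at 2%, the sum is 38% and 27 x 0.38 = 10.3. Events that the present rule already records come off these totals. Scheduled tests with no quoted Grade 3-4 rate, such as calcium, could add a few.
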